7.0 Trial Objectives

7.1 Primary Objective

The primary objective of the trial is:

• To demonstrate the efficacy of HIL-214 vaccine against moderate/severe (mod/sev) AGE associated only with GI.1 or GII.4 NoV genotypes.

7.2 Secondary Objectives

7.2.1 Key Secondary Efficacy Objective

The key secondary efficacy objective of the trial is:

To evaluate the efficacy of HIL-214 vaccine against mod/sev AGE associated only with any NoV (GI or GII) genotypes.

7.2.2 Secondary Efficacy Objectives

The other secondary efficacy objectives of the trial include:

- To evaluate the efficacy of HIL-214 vaccine against mod/sev AGE associated with GI.1 or GII.4 NoV genotypes, irrespective of other gastroenteritis (GE) pathogens.
- To evaluate the efficacy of HIL-214 vaccine against mod/sev AGE associated with any NoV genogroup (GI or GII), irrespective other GE pathogens.

7.2.3 Secondary Immunogenicity Objectives

• To evaluate the immunogenicity of HIL-214 vaccine.

7.2.4 Secondary Safety Objective

The secondary safety objective of the trial is:

• To assess the safety of HIL-214 vaccine compared to placebo.

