#### Primary hypothesis:

The primary hypothesis for this phase 2b proof-of-concept trial is that HIL-214, administered as 2-dose regimen, provides protection against moderate and severe AGE associated only with GI.1 or GII.4 vaccine-represented norovirus genotypes in the targeted population of infants.

This phase 2b trial aims to demonstrate the vaccine efficacy (VE) of two doses of HIL-214 administered up to 8 weeks apart, against moderate or severe AGE due to GI.1 or GII.4 norovirus genotypes in approximately 3000 healthy children aged 5 months at the time of the first dose up to when they reach the age of 2 years, as well as the safety and immunogenicity of HIL-214. A placebo arm is included to allow an unbiased evaluation of efficacy and safety. Placebo will be used in this trial because there is no single active comparator vaccine that is available across all participating sites.

The trial will be conducted in accordance with this protocol, International Council for Harmonisation of Technical Requirements for Pharmaceuticals for Human Use (ICH), Good Clinical Practice (GCP) Guidelines, and applicable regulatory requirements.

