# **OBJECTIVES AND ENDPOINTS (continued)**

Secondary Safety Objectives		
• To assess the safety of HIL-214 compared to placebo.	
 
Solicited local AEs up to 7 days after each dose of trial vaccine.
 
Solicited systemic AEs up to 7 days after each dose of trial vaccine.
 
Unsolicited AEs for up to 28 days after each dose of trial vaccine.
 
AEs leading to trial vaccine dose withdrawal.
 
AEs leading to the subject's withdrawal from the trial from Day 1 to the end of the trial.
 
	
 
Proportion of subjects with, and number of:
 
Local reactions.
 
Systemic solicited AEs.
 
Unsolicited AEs.
 
AEs leading to trial vaccine dose withdrawal.
 
AEs leading to the subject's withdrawal from the trial.
 
SAEs.
 

Exploratory Objectives	SAEs throughout the trial.	In the SAF.

HIL-214	
Trial No. NOR-212	Page 44 of 100
Protocol DOC-00351, 3.0	1 September 2023

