11.0 Statistical Methods

All statistical analyses will be performed using SAS® Version 9.4 or higher.

Unless otherwise noted, continuous variables will be summarized using the number of observations (n), mean, standard deviation, median, first quartile (Q1), third quartile (Q3), minimum, and maximum values. The minimum and maximum values will be displayed to the same level of precision as the raw data; the mean, median, Q1 and Q3 values to one additional decimal place and the standard deviation to two additional decimal places.

Categorical variables will be summarized using counts and percentages. Percentages will be rounded to one decimal place, except 100% will be displayed without any decimal places, and percentages will not be displayed for zero counts.

Listings will be provided for relevant summaries.

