12.1 Adverse Events

Unsolicited adverse events will be coded according to the MedDRA version 24.1.

An overall summary of the number of patients with AEs after first dose of trial vaccine and number of events will be summarized, with line items for each of the following:

- Solicited local AEs
- Solicited systemic AEs
- Unsolicited AEs
- SAEs
- AEs leading to trial vaccine dose withdrawal
- AEs leading to withdrawal from the trial.

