12.1.3 Unsolicited Adverse Events

The number and percentage of subjects experiencing any unsolicited AE (up to 28 days after each vaccine dose) will be summarized by trial arm, and by SOC and PT. Unsolicited AE summaries will include solicited AEs ongoing after 7 days post-vaccination. Percentages will be calculated based on the number of subjects in the SAF.

Unsolicited AEs will further be summarized by relationship to the trial vaccine or trial procedure. Subjects with multiple events coding to the same SOC or PT will be counted only once in that level, according to the most related event.

Unsolicited AEs will similarly be summarized by severity to the trial vaccine. Subjects with multiple events coding to the same SOC or PT will be counted only once in that level, according to the most severe event.

Unsolicited AEs after each vaccination will be summarized in the following 3 ways: 1) overall for Day 1 (day of vaccination) to 28 days after each vaccination, 2) with onset between Day 1 (day of vaccination) and Day 7 after each vaccination, and 3) with onset between Day 8 and Day 28 after each vaccination. Each group will be summarized after each vaccine dose, and any vaccine dose by trial arm and overall.

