12.1.4 Deaths and Serious Adverse Events

SAEs and fatal SAEs occurring after each dose and after any dose will be summarized by vaccine dose and overall, by SOC and PT. Summaries will be provided by trial arm and overall. Percentages will be calculated based on the number of subjects in the SAF.

SAEs including fatal SAEs will be included in a subject listing.

SAEs and fatal SAEs will similarly be summarized by relationship and by severity as described for unsolicited events above.

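### The safety objective is a comparison with placebo, but the plan pre-specifies only by-arm descriptive summaries and no vaccine-placebo difference or interval

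*SAP*

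**What the plan says.** Both documents name placebo as the comparator for safety. SAP 7.2.4 has "To assess the safety of HIL-214 vaccine compared to placebo"; Protocol 5.0 has "To assess the safety of HIL-214 compared to placebo". The protocol also gives safety as part of the reason for having a control arm: "A placebo arm is included to allow an unbiased evaluation of efficacy and safety" (Trial Summary, Primary hypothesis, repeated in 4.2).

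The statistic for this objective is set in the protocol's objectives table, in the safety row: "Proportion of subjects with, and number of" each class of event, in the safety set (SAF). The SAP follows that:

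- General rule, SAP 11.0: "Categorical variables will be summarized using counts and percentages".
- SAP 12.1: "An overall summary of the number of patients with AEs after first dose of trial vaccine and number of events will be summarized", with six lines (solicited local, solicited systemic, unsolicited, serious, leading to dose withdrawal, leading to trial withdrawal).
- SAP 12.1.1 and 12.1.2: numbers and percentages for solicited events and temperature categories, with subjects having at least one non-missing assessment as the denominator.
- SAP 12.1.3: numbers and percentages for unsolicited events by arm; "Percentages will be calculated based on the number of subjects in the SAF".
- SAP 12.1.4: "SAEs and fatal SAEs occurring after each dose and after any dose will be summarized by vaccine dose and overall, by SOC and PT", by arm and overall. SAP 12.1.5 and 12.1.6 treat the two withdrawal categories in a similar way.
- SAP 12.2: mean, SD, median, quartiles and range for growth and vital signs.

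Protocol 13.1.5 agrees, and adds day of first onset and number of days with each solicited event.

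**The concern.** The objective asks how safety under HIL-214 compares with safety under placebo. The planned output describes each arm and leaves the comparison to the reader.

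This matters because several solicited events (fever, irritability, vomiting, diarrhea) can also arise in infants for reasons unrelated to vaccination. The excess over placebo therefore carries the safety information. Two proportions side by side show neither how well that excess is estimated nor how large an excess the data leave open. A reader of the report would have to derive both, probably without the country stratification used at randomisation. Any contrast that the sponsor added later would be chosen after unblinding.

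**Working it through.** **Check of the text.** SAP 12.1 to 12.2 and Protocol 13.1.5 were read for any between-arm difference, ratio, interval or test. There is none. These sections are readable, so the blacked-out exploratory text does not explain the absence. Intervals are planned elsewhere, but they differ in kind:

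| Quantity | Where | Type of interval |
|---|---|---|
| Vaccine efficacy | SAP 11.5.3.1, 11.5.3.3 | Between arms |
| Seroresponse rate | SAP 11.6.1 | Within arm (Clopper-Pearson) |
| GMC, GMFR | SAP 9.5.3, 9.5.4 | Within group |
| Laboratory agreement (kappa) | SAP 9.3.4 | Not an arm contrast |
| Adverse events | SAP 12.1 | None |

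**Plan's own figure.** There is none for safety. The only power statement (SAP 8.1) concerns the primary efficacy endpoint and does not bear on this point.

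**What precision was available.** Inputs: 1500 per arm (SAP 8.0). The event rates *p* are assumed, because the documents give none. For equal rates in both arms:

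half-width = 1.96 × √(2p(1 − p)/1500)

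- p = 2%: 1.96 × √(0.0392/1500) = 1.00 point
- p = 5%: 1.96 × √(0.0950/1500) = 1.56 points
- p = 10%: 1.96 × √(0.1800/1500) = 2.15 points

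Newcombe score intervals at the same rates give ±1.03, ±1.57 and ±2.15, so the choice of method matters little here.

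If the denominator were 30% smaller (1050 per arm, taking the upper end of the 20% to 30% range that SAP 8.1 gives for drop-out and non-evaluable samples as a pessimistic bound), each half-width grows by √(1500/1050) = 1.195, to about 1.2, 1.9 and 2.6 points.

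**Illustration with assumed counts.** Suppose 75/1500 children on HIL-214 and 60/1500 on placebo have a serious event.

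- Planned table: 75 (5.0%) and 60 (4.0%).
- Risk difference: 5.0 − 4.0 = +1.0 point. SE = √[(0.05 × 0.95 + 0.04 × 0.96)/1500] = 0.757 point. 95% CI: 1.0 ± 1.96 × 0.757 = −0.48 to +2.48.
- Risk ratio: 75/60 = 1.25. SE of log = √(1/75 − 1/1500 + 1/60 − 1/1500) = 0.169. 95% CI: 0.90 to 1.74.

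The interval adds that the data are compatible with no excess and with an excess of up to about 2.5 points. It is computed entirely from numbers that the planned tables already hold.

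**The case against.** The strongest reply is that the protocol defines how this objective is to be answered. The row that names placebo as comparator also names the statistic, proportion and number, and the SAP delivers exactly that. A reader might infer that objective and analysis contradict each other. They do not: objective, statistic and output line up, and side-by-side presentation by arm is one form of comparison. This stands. The point is that a more informative analysis is available, not that the documents conflict.

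A reader might also infer that the trial can never yield a vaccine-placebo difference, or that every safety output is a percentage. Neither is supported. Counts accompany the percentages, and the SAP reports the size of each analysis set (11.1), so a crude difference can be derived. SAP 5.0 allows unplanned analyses if identified as such. Vital signs, growth, day of onset and duration are summarised in other ways. What can be said is that no contrast is pre-specified.

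Nor do the seroresponse, GMC and GMFR intervals show that safety was singled out. They are within-arm, and in the readable text only efficacy has a between-arm estimate.

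Finally, the documents state no safety hypothesis, so nothing calls for a test. That is right, and none is proposed. The event rates used above are assumed, and the example does not show a conclusion that would change.

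**Conclusion.** The point holds as a cheap improvement. The objective is comparative, the safety plan is descriptive by arm, and no estimate of the excess over placebo or of its precision is pre-specified. The gap lies in the plan and not in the sample size: 1500 per arm would give intervals of about ±1.0, ±1.6 and ±2.2 points at assumed rates of 2%, 5% and 10%. Those widths rest on assumed equal rates, full denominators and unstratified intervals; real rates and missing assessments will shift them. The primary efficacy conclusion is not affected, and the existing safety tables remain valid for what they show.

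**What to change.** In SAP 12.1, add the HIL-214 minus placebo risk difference with a 95% CI for the proportion of subjects:

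- in each of the six lines of the overall adverse event summary; and
- for grade 3 solicited events.

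Use the SAF by vaccine received, with the rule in SAP 9.1.1 for children who received one dose of each product. Keep the SAP's own denominators: the SAF in general and, for solicited events, subjects with at least one non-missing assessment. Use the Miettinen-Nurminen method stratified by country, and state that the unstratified form applies where events are too sparse. Label the intervals as descriptive estimates, without tests or multiplicity control. Leave the SOC and PT tables as counts and percentages.

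The cost is a short SAP paragraph and added columns in existing tables; no new data are needed. The downside is several unadjusted intervals. If grade 3 is shown for each of the nine graded solicited events in Protocol Table 10.b, there are 6 + 9 = 15 intervals for an any-dose summary. With no true difference anywhere, about 15 × 0.05 = 0.75 of them would be expected to exclude zero by chance. The descriptive label should say so.

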7.3 Exploratory Objectives

7.3.1 Exploratory

7.3.2 Exploratory	
7.3.3 Exploratory	
7.3.4 Exploratory	
7.3.5 Exploratory	
7.3.6 Exploratory	
7.3.7	

8.0 Trial Design

This is a phase 2b, double-blind, randomized, multi-site, placebo-controlled trial to evaluate the efficacy, safety, and immunogenicity of two doses of the intramuscular (IM) HIL-214 vaccine compared to placebo in approximately 3000 children, 5 months of age (-14/+14 days) at the time of the first dose of trial vaccine.

The second dose of trial vaccine should be administered 28 days (and up to 56 days) after the first dose. Trial vaccine doses will be given at least 14 days before or after non-live and orally administered live vaccines, and at least 28 days before or after parenterally administered live vaccines which are given in accordance with country pediatric immunization guidelines. Subjects will be allocated (1:1) into 1 of 2 trial arms by interactive response technology (IRT), stratified by country:

- Arm 1 (N = 1500): One dose of HIL-214 t Visit 1 (Day 1) and one dose of HIL-214 at Visit 2 (28 to 56 days post dose 1)
- Arm 2 (N = 1500): One dose of placebo at Visit 1 (Day 1) and one dose of placebo at Visit 2 (28 to 56 days post dose 1).

A schematic of the Trial Design can be found in Section 6.1 of the protocol.

8.1 Determination of Sample Size

Collection of 24 primary endpoint cases will provide a power greater than 80% in comparing active vaccine versus placebo in the rate of evaluable first-confirmed AGE cases (moderate or severe) associated with norovirus GI.1 or GII.4 without co-pathogens during the 6 months period if the true vaccine efficacy (VE) is 70%. The underlying assumptions are a 7% annual incidence of moderate to severe AGE attributable to norovirus GI.1 or GII.4, hypothesizing that 40% of norovirus AGE cases are moderate to severe, and 30% are associated with norovirus GI.1 or GII.4 resulting in the 6-month incidence of evaluable primary endpoint AGE cases of 3.5%.

It is expected that enrollment of 3000 subjects will provide sufficient number of cases to demonstrate efficacy, accounting for various rates of drop-out/non-evaluable samples (20% to 30%), and possible lower incidence rate or underreporting of cases.

8.2 Randomization

Subjects who meet all inclusion criteria and none of the exclusion criteria will be centrally randomized in accordance with a computer-generated randomization schedule. Approximately 3000 subjects will be allocated (1:1) into 1 of 2 trial arms, HIL-214 vaccine and placebo, by IRT. Randomization will be stratified by country.

9.0 Objectives and Endpoints

ກ່	9.0 Ubjectives and Endpoints				
Ρ	Primary Objective	En	Endpoints	Sul	Summary Statistics and Analysis Sets
•	To demonstrate the efficacy of HIL-214	•	Time to first occurrence during the primary	•	VE estimate** (VE; calculated as 100X [1
	vaccine against mod/sev AGE associated only		observation period*, of mod/sev AGE case		minus the risk ratio of AGE cases according to
	with GI.1 or GII.4 NoV genotypes.		associated only with GI.1 or GII.4 NoV		the endpoint definition in the vaccine group
			genotypes.		over that in the placebo group]) in the mFAS.
Ň	Secondary Objectives				
K	Key Secondary Efficacy Objective				
٠	To evaluate the efficacy of HIL-214 vaccine	•	Time to first occurrence during the primary	•	VE estimate according to the endpoint
	against mod/sev AGE associated only with		observation period* of mod/sev AGE case		definition, in the mFAS.
	any NoV (GI or GII) genotypes.		associated only with any NoV (GI or GII)		
			genotypes.		
Š	Secondary Efficacy Objectives				
٠	To evaluate the efficacy of HIL-214 vaccine	•	Time to first occurrence during the primary	٠	VE estimate according to the endpoint
	against mod/sev AGE associated with GI.1 or		observation period* of mod/sev AGE case		definition, in the mFAS.
	GII.4 NoV genotypes, irrespective of other		associated with GI.1 or GII.4 NoV genotypes,		
	GE pathogens.		irrespective of other GE pathogens.		
٠	To evaluate the efficacy of HIL-214 vaccine	•	Time to first occurrence during the primary	•	VE estimate according to the endpoint
	against mod/sev AGE associated with any		observation period* of mod/sev AGE case		definition, in the mFAS.
	NoV genogroup (GI or GII), irrespective of		associated with any NoV genogroup (GI or		
	other GE pathogens.		GII), irrespective of other GE pathogens.		
Ñ	Secondary Immunogenicity Objectives				
٠	To evaluate the immunogenicity of HIL-214.	•	Pre-dose 1, 28 days post dose 1, and	•	GI.1 GMCs, GMFRs and SRRs at relevant
			28 days post dose 2:		time points.
		•	HBGA blocking antibody concentrations.	•	GII.4 GMCs GMFRs and SRRs at relevant
		•	Pan-Ig antibody concentrations.		time points.
				In 1	In the FAS and PPS-I.

Page 10 of 44

_
ned
contii
\mathbf{z}
ENDPOINTS
(DE)
A
IVES
OBJECTI

Page 11 of 44

OBJECTIVES AND ENDPOINTS (continued)

Abbreviations: AE, adverse event; AGE, acute gastroenteritis; CI, confidence interval; GE, gastroenteritis; GMFR, geometric mean fold rise; GMC, geometric

mod, moderate; mFAS, modified Full-Analysis set; NoV, norovirus; pan-Ig, total immunoglobulin; PPS, Per-Protocol set; SAE, serious adverse event; SAF, Safety-Analysis set; sev, mean concentration; HBGA, histoblood group antigen; severe; SRR, seroresponse rate.

Notes on the next page.

Page 12 of 44

	HILLEVAX
	Statistical Analysis Plan (SAP) Version Date: 05-JUN-2024 Sponsor: Hillevax Protocol No: NOR-212
Subject age at trial entry is 5 months (-14/+14 days). *The duration of the primary observation period is 6 months starting at 28 days post-Dose 2. Time-to-event will be computed from the start of the observation period until the date of AGE onset; the date of last contact/discontinuation; the end of the observation period, whichever is earlier. **Vaccine efficacy will be demonstrated if the lower limit of the 95.0% CI is above 0%.	the start of
 AGE Case Definition and Severity Assessment: All subjects meeting the following criteria indicating clinical illness (i.e., AGE) will be included in the efficacy analysis: Individuals presenting with at least three loose or liquid stools OR at least two or more episodes of vomiting OR one or more loose or liquid stools on the context of the context of the context of the stools of the context of t	e efficacy analysis: pisodes of vomiting OR one or more loose or liquid stools
The severity assessment of AGE episodes will be determined based on a modified Vesikari score (MVS) Appendix A Recurrent norovirus AGE in a subject is considered a new illness according to the clinical AGE definition if: The subject has been free from clinical symptoms for at least 5 consecutive days.	/S) Appendix A . tion if:
jed	Page 13 of 44

9.1 Analysis Sets

9.1.1 Safety Analysis Set (SAF)

The SAF will consist of all subjects who are randomized and received at least one dose of HIL-214 or placebo. Subjects will be analyzed according to the trial vaccine which they actually received.

Data from subjects who received one dose of HIL-214 and one dose of placebo will be analyzed in the HIL-214 group for summaries after corresponding HIL-214 dose and summaries after any dose, and in placebo group for summaries after the dose of placebo.

A subject may be excluded from the SAF due to major Good Clinical Practice violations.

9.1.2 Full Analysis Set (FAS)

The FAS will include all subjects who are randomized and received at least 1 dose of HIL-214 or placebo. Subjects will be analyzed according to their randomized trial arm.

A subject may be excluded from the FAS due to major Good Clinical Practice violations.

9.1.3 Modified Full Analysis Set - Efficacy Evaluable Subjects (mFAS)

The mFAS will include all subjects who are randomized and received 2 doses of HIL-214 or placebo. Subjects will be analyzed according to their randomized trial arm.

A subject may be excluded from the mFAS due to major Good Clinical Practice violations.

9.1.4 Efficacy Per-Protocol Analysis Set (PPS-E)

The PPS-E will include all subjects in the mFAS who have no important protocol deviations which may affect the evaluation of efficacy. These categories of important protocol deviations include: (1) not meeting selected entry criteria, (2) receiving wrong or incomplete trial product (3) receiving prohibited therapies, and (4) other important protocol deviations that may affect evaluation of efficacy. Subjects will be analyzed according to the trial vaccine which they actually received.

9.1.5 Immunogenicity Per-Protocol Analysis Set (PPS-I)

The PPS-I will include all subjects in the mFAS with a baseline blood sample collected before administration of first dose and who have no important protocol deviations which may affect evaluation of immunogenicity. These categories of important protocol deviations include: (1) not meeting selected entry criteria, (2) receiving wrong or incomplete trial product (3) receiving prohibited therapies, (4) protocol-described regimen not followed for storage of investigational vaccine or placebo, (5) vaccination regimen described in protocol not followed for administration of investigation vaccine or placebo, (e.g., administered out of window, or in incorrect injection site) and (6) other important protocol deviations that may affect evaluation of the immunogenicity. Subjects will be analyzed according to the trial vaccine which they actually received.

9.2 Conventions and Derivations

9.2.1 Baseline and Change from Baseline

Unless otherwise specified, baseline is defined as the last non-missing value before the first dose of trial vaccine (HIL-214 or Placebo). Baseline values will be collected at the Day 1 visit in this trial, prior to the administration of the study injection. Change from baseline is defined as (value at post-baseline visit – value at baseline). Baseline is set to missing if no dose of trial vaccine is administered.

